15.7 Missing Data

Whenever possible, statistical methods such as linear mixed-effects modeling which naturally handle missing data will be utilized. Missing data will be investigated carefully by the biostatistician, the study manager and the clinical staff to assess its probable cause, and whether missing not at random (MNAR, missingness dependent on outcome), missing at random (MAR, missingness not dependent

on outcome but can be fully accounted for by other non-missing covariates) or missing completely at random (MCAR, missingness independent of both observed variables and unobserved parameters of interest) is most likely.

If any missing data patterns are determined to be MNAR, this observance will be reported narratively in the final report(s) and publication(s), and no imputation methods will be pursued. Little's test will be used to assess whether missing values are missing completely at random (MCAR). For methods that require complete data or listwise deletion (e.g. PCA), and where missing data is determined to be reasonably missing at random (MAR or MCAR), multiple imputation using predictive mean matching will be employed.

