15.5.2.4 Conversion to Secondary Interventions

In important endpoint for subjects enrolled in this study will be conversion to alternative treatments. The protocol allows for a single intra-articular corticosteroid injection into the knee to manage knee pain without necessitating removal of the subject from the study. However, if a study subjects elects to convert to a regenerative medicine treatment (e.g. platelet rich plasma or bone marrow aspirate concentrate) or a surgical intervention (e.g. microfracture or total joint replacement), they will be removed from the study. Cox proportional hazards regression will be performed to compare the hazard rate of conversion to each of these two treatment categories between treatment groups.

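### Section 15.7 can label dropout driven by recorded scores as MNAR and then bar imputation, leaving the PRO and function comparisons on completers, and no endpoint has a quantitative MNAR check

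*Combined protocol and SAP*

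**What the plan says.** Section 15.7 sorts missing data into three kinds and acts on the label.

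- **MNAR** is given as "missing not at random (MNAR, missingness dependent on outcome").
- **MAR** is missingness that does not depend "on outcome but can be fully accounted for by other non-missing covariates".
- **If MNAR, reporting:** "If any missing data patterns are determined to be MNAR, this observance will be reported narratively in the final report(s) and publication(s").
- **If MNAR, imputation:** the same sentence closes it off with the words "and no imputation methods will be pursued".
- **If MAR or MCAR**, for methods that need complete data: "where missing data is determined to be reasonably missing at random (MAR or MCAR), multiple imputation using predictive mean matching will be employed".
- **The only formal test:** "Little's test will be used to assess whether missing values are missing completely at random (MCAR").
- **The general preference:** "Whenever possible, statistical methods such as linear mixed-effects modeling which naturally handle missing data will be utilized".

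Section 15.4 promises an intent-to-treat analysis and says listwise deletion will be avoided as far as possible. Section 15.5.2.4 says of subjects who convert to a regenerative or surgical treatment that "they will be removed from the study". It compares conversion between arms by Cox regression. Section 15.6 plans for 20% dropout or incomplete follow-up.

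**The concern.** In standard usage, MAR allows missingness to depend on anything observed, including the subject's own earlier outcome values. MNAR means that missingness still depends on the unseen value after the observed data are taken into account. Section 15.7 draws the line elsewhere: any dependence on outcome is MNAR. A subject who reports a poor score at six months and then leaves is a MAR case, and a mixed model or imputation using the six-month score can handle it. Under the plan's wording the same case is MNAR, and imputation is not allowed.

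Two things are at stake. Analyses that need a value at the visit would drop such subjects, contrary to the aim in Section 15.4. For dropout that really is MNAR, the reader gets a narrative with no indication of how far the result could move. The protocol itself supplies a route for outcome-related dropout, because subjects who convert leave the study and a poor knee is a foreseeable reason to convert.

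**Working it through.** **1. Which analyses the bar reaches**

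| Endpoint | Section | Method | Effect of barring imputation |
|---|---|---|---|
| MRI T2, T1rho | 15.5.2.1 | Random-intercept mixed model | None; uses all recorded visits |
| NRS pain, first 3 months | 15.5.2.3 | Random-intercept mixed model | None; uses all recorded scores |
| IKDC, WOMAC, Tegner, Lysholm | 15.5.2.3 | ANCOVA at each time point, baseline as covariate | Completers at that visit; intermediate scores unused |
| Kinematics, strength, function | 15.5.2.2 | Welch's t-test | Completers at that visit |
| Conversion | 15.5.2.4 | Cox regression | Not affected |

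Little's test cannot rescue the label. If dropout depends on a recorded score the data are not MCAR, and a rejection leaves MAR and MNAR to be told apart by judgement under the definitions above. Observed data cannot separate the two.

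**2. The plan's own figure**

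Section 15.7 gives none. The sample size in Section 15.6 (SMD 0.73, two-sided alpha 0.05, 80% power) reproduces: n = 2 × (1.960 + 0.842)² / 0.73² = 29.5, so 30 per group. The exact t calculation gives 79.4% power at 30 and needs 31.

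**3. Dropout that depends on recorded scores (simulated; all settings assumed)**

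*Setting A.* Baseline, 6 and 12 months; correlation 0.6; true difference 0.73 SD; the same dependence on score in both arms (logit slope 1.2 per SD); 26% missing (about 33% placebo, 19% fisetin); 36 or 50 per arm.

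| Dropout driven by | Completers' ANCOVA | MAR method using 6-month score |
|---|---|---|
| Recorded 6-month value | 0.70 | 0.73 |
| Unrecorded 12-month value | 0.64–0.65 | 0.65–0.66 |

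In the first row the completers' bias is (0.73 − 0.70)/0.73 = 4%, and the MAR method removes it. In the second row neither method recovers 0.73.

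*Setting B.* 36 per arm; four post-baseline visits; correlation 0.7; true difference 0.50 SD; dropout before each visit depends on the previous recorded score, with a logit slope of 1 or 1.5 per SD.

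| Base dropout per visit | Arms where score matters | Missing at last visit | Completers' ANCOVA | Bias towards null |
|---|---|---|---|---|
| 7% | Placebo only | Placebo 32–37%, fisetin 25% | 0.45 to 0.42 | 10–17% |
| 7% | Both, same slope | Placebo 32–37%, fisetin 25–27% | 0.49 to 0.47 | 2–6% |
| 4% | Placebo only, slope 1 | Placebo 21%, fisetin 15% | 0.47 | 6% |
| 4% | Placebo only, slope 1.5 | Placebo 26%, fisetin 15% (21% overall) | 0.45 | 10% |
| 4% | Both, same slope | 18–22% overall | 0.49 to 0.48 | 2–4% |

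A MAR method using the recorded scores gives 0.50 in every row. The standard deviation of a single trial's estimate is about 0.20, well above any of these biases.

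**4. What a delta-adjusted analysis would report**

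Let m be the fraction missing and δ the amount, in SD, by which fisetin dropouts are worse than modelled. The difference falls by m × δ. With m = 0.20 and δ = 1, that is 0.20 SD, or 0.20/0.73 = 27% of the target.

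- 36 per arm: 36 × 0.8 = 28.8 completers, so the smallest significant difference is about 2.00 × √(2/28.8) = 0.53 SD. A completers' difference of 0.73 loses significance at δ = (0.73 − 0.528)/0.20 = 1.0 SD.
- 50 per arm (the cap of 100): 40 completers, threshold 0.445 SD, tipping δ = (0.73 − 0.445)/0.20 = 1.4 SD.
- From 10% to 30% missing, the tipping δ runs from 2.3 to 0.55 SD (36 per arm) and from 3.1 to 0.84 SD (50 per arm).

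These figures hold the standard error at the completers' value and shift one arm only. Equal dropout with equal shifts in both arms cancels.

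**The case against.** The strongest defence is that the sentence bars imputation only. A reader might infer that all efficacy analyses collapse to complete cases. The documents do not support that: Section 15.7 prefers mixed models, and the MRI and NRS models run whatever label is attached. Under a correctly specified model they remain valid when dropout depends on recorded scores. This stands, and it confines the completers problem to the PRO ANCOVAs and the Welch tests.

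A reader might also take 10–17% as the size of the defect. The top of that range needs dropout to depend on score in the placebo arm alone, with placebo missingness well above the plan's 20%. The figure also measures the loss from per-visit ANCOVA under MAR dropout, so it says nothing about truly MNAR data. In these settings the bias runs against fisetin.

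A third tempting reading is that conversion is left to narrative. It is not: it is a secondary endpoint with its own Cox comparison. That comparison does not, however, show how removing converters affects the PRO, function or MRI estimates.

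The definitions can also be read charitably. Outcome may mean the missing value itself, and the non-missing covariates may include earlier scores. On that reading the mislabelling disappears, but the wording does not say so, and the lack of a quantitative check remains. Declining MAR imputation under true MNAR is defensible, since it gains little (0.65–0.66 against 0.64–0.65 in setting A). Narrative alone is a weak substitute for a sensitivity analysis.

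Finally, the primary endpoint is adverse events in a small Phase I/II trial. That limits the weight of the point without removing it.

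**Conclusion.** The point holds in a limited form. As written, Section 15.7 can classify dropout driven by recorded scores as MNAR, and its imputation bar then leaves the per-visit PRO ANCOVAs and the function and strength Welch tests on completers. No endpoint has a quantitative check for true MNAR.

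The likely bias from the first problem is modest. It is about 2–6% towards the null when score affects dropout equally in both arms, or when a moderate placebo-only dependence goes with dropout near 20%. It is about 10% with a steeper placebo-only dependence near 20% overall, and up to about 17% only with placebo-only dependence and 32–37% placebo missingness. Under true MNAR the direction and size are unknown. Only the 20% dropout, the 0.73 SD target and the group sizes come from the documents; correlations, slopes, shifts and the 0.50 SD effect are assumptions. The affected results are secondary efficacy endpoints, so this should be corrected but does not threaten the primary safety analysis.

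**What to change.** 1. In Section 15.7, define MAR as missingness that may depend on observed data, including earlier outcome values, and MNAR as missingness that depends on unobserved values given the observed data.
2. Delete the clause that rules out imputation.
3. In Sections 15.5.2.2 and 15.5.2.3, analyse function, strength and the PRO scales with a repeated-measures mixed model, or with multiple imputation that uses earlier scores.
4. Prespecify one delta-adjusted (tipping-point) sensitivity analysis for the main MRI and PRO comparisons, covering data missing after conversion, with the range of shifts fixed before group labels are attached to the data.

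The cost is SAP wording and a modest amount of extra work in R, with no new data, visits or subjects. The downside is that the range of shifts must be chosen and justified in advance.

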15.8 Data Preparation and Maintenance of Blinding

The study manager will direct the data compilation steps of various team members according to consultation with the senior biostatistician. Gathering of partial midpoint data will be performed at reporting milestones throughout the study, but no statistical inference testing will be conducted until study completion. Research scientists, engineers, clinicians and database managers will assemble their respective data spreadsheet using the patient ID number and will remain blinded to treatment group allocation throughout this process. As a final step before data analysis, group allocation will be added to the research spreadsheets, but this will be limited to "Group A" and "Group B". The full statistical analysis will be performed prior to unblinding which group received the FIS supplement.

16.0 Principal Investigator's Ethical and Regulatory Obligations

The Principal Investigator is responsible for ensuring that the trial is conducted according to the signed investigator statement, the study protocol and applicable regulations; for protecting the rights, safety, and welfare of subjects under the investigator's care; and for the control of the Study Medication. The Principal Investigator shall confirm informed consent for each subject to whom Fisetin (FIS) or placebo, is administered. A discussion of the Principal Investigator's minimal responsibilities follows.

16.1 Study Conduct: Ethics and Good Clinical Practice

Principal Investigator will administer Study Medication only to subjects under his personal supervision or under the supervision of an appropriate Study Team designee responsible to the Principal Investigator.

This study must be carried out in compliance with the protocol and in accordance with the Good Clinical Practice, ICH Guidelines and the Declaration of Helsinki, concerning medical research in humans (Recommendations Guiding Physicians in Biomedical Research Involving Human Subjects, Helsinki 1964, amended Tokyo 1975, Venice 1983, Hong Kong 1989, Somerset West 1996).

The Principal Investigator agrees, when signing the protocol, to adhere to the instructions and procedures described in it and thereby to adhere to the applicable regulatory requirements and to the principles of Good Clinical Practice to which it conforms.

16.2 Institutional Review Board

The Principal Investigator shall assure that an IRB that complies with the requirements set forth in ICH and FDA guidelines will be responsible for the initial and continuing review and approval of the proposed clinical study. The Principal Investigator shall also ensure that he or she will promptly report to the IRB all changes in the research activity and all unanticipated problems involving risk to human subjects or others. Except when the changes constitute minor administrative ones or where necessary to eliminate apparent immediate hazards to human subjects, the Principal Investigator will not make any changes in the research without IRB approval.

Before implementing this study, the protocol, the proposed informed consent form and other subject information, must be reviewed and approved by the Institutional Review Board (IRB).

Other Principal Investigator responsibilities relative to the IRB include the following:

- Submit all protocol amendments to the IRB for review;
- Report to the IRB any information about serious AEs reported in other studies associated with treatment;
- Provide the IRB with any other information it requests before or during the conduct of the study;
- Report to the IRB all adverse events as required by the approving IRB(s);
- Maintain a file of IRB/study-related information;
- Update the IRB on a minimum of a yearly basis;
- Maintain IRB approval during the duration of the study.

16.3 Informed Consent

Principal Investigators must explain to each subject the nature of the study, its purpose, the procedures involved, the expected duration, the potential risks and benefits involved and any discomfort it may entail. Each subject must be informed that participation in the study is voluntary and that he or she may withdraw from the study at any time and that withdrawal of consent will not affect his or her subsequent medical treatment or relationship with the treating physician.

This informed consent should be given by means of a standard written statement, written in non-technical language. The subject should read and consider the statement before signing and dating it and should be given a copy of the signed document.

No subject can enter the study before his/her informed consent has been obtained.

The Informed Consent Form must be submitted by the Principal Investigator for IRB approval.

16.4 Record Keeping and Study Documents

Study documents used to record demographic, procedural, and follow-up data, as well as any adverse clinical events that may occur during the study must be retained by the Principal Investigator.

The Principal Investigator must verify personal oversight of the clinical trial and confirm that all data recorded is accurate and current.

All data entries must be made only by the Principal Investigator and/or other site trained personnel. Training will be documented and logged in the site study binder.

16.4.1 Study Medication Accountability

It is the responsibility of the Principal Investigator to ensure that all Study Medication is inventoried and strictly accounted for throughout the study. This accounting is to be recorded in appropriate documents kept at the clinical site.

16.4.2 Study Documents

The investigator/institution should maintain adequate and accurate source documents and trial records that include all pertinent observations on each of the site's trial subjects. Source data should be attributable, legible, contemporaneous, original, accurate, and complete. Changes to source data should be traceable, should not obscure the original entry, and should be explained if necessary (e.g., via an audit trail).

16.4.3 Records Retention

All correspondence related to this clinical study should be kept in appropriate study files at the clinical site. Records of subjects, study documents, product inventory, and IRB and Study Team correspondence pertaining to the study must also be kept on file.

The Principal Investigator must retain Essential Study Documents including: protocols, amendments, IRB/EC approvals, signed and dated consent forms, source documents, medical records, case report forms, device accountability records, all correspondence and all other documents pertaining to the conduct of the study.

16.4.4 Records/Reports Inspection

Investigator sites and study documentation may be subject to Quality Assurance (QA) audits during the course of the study. In addition, inspections may be conducted by regulatory bodies at their discretion, during and after study completion.

The Investigator agrees to allow inspectors from regulatory agencies to have access to all study records, including subject source documents. By participating in this study, the Investigators agree to these requirements and will assist the inspectors in their duties. The Investigator should immediately notify the Sponsor of an upcoming inspection.

Investigators shall upon request from any properly authorized officer or employee of FDA, at reasonable times, permit such officer or employee to have access to, and copy and verify any records or reports made by the Investigator pursuant to CFR 312.62. The Investigator is not required to divulge subject names unless the records of particular individuals require a more detailed study of the cases, or unless there is reason to believe that the records do not represent actual case studies, or do not represent actual results obtained.

16.4.5 Study Oversight

The investigator is responsible for supervising any individual or party to whom the Principal Investigator delegates trial-related duties and functions conducted at the trial site.

If the investigator/institution retains the services of any individual or party to perform trial-related duties and functions, the investigator/institution will ensure this individual or party is qualified to perform those trial-related duties and functions and will implement procedures to ensure the integrity of the trial-related duties and functions performed and any data generated.

16.4.6 Interim and Final Study Reports

The Principal Investigator shall furnish all progress reports required by applicable regulations the FDA, IRB and to the Medical Monitor including an analysis of data reported.

16.4.7 Publication Plan

The Principal Investigator holds the primary responsibility for publication of the results of the study. We will register with ClinicalTrials.gov within 21 days of enrollment of the first participant. We will post results to ClinicalTrials.gov within 12 months of final data collection for the primary outcome.

17.0 Monitoring of Study

The primary goal of study monitoring is to protect subject safety. The study monitoring program will apply a risk-based approach to ensure that:

1. All treatment emergent adverse events are accurately recorded;
2. The rights and well-being of the human subjects are being protected;
3. The reported data are accurate, complete, and verifiable from source documents;
4. The conduct of the study complies with the currently approved protocol and any amendments, and in accordance with all local, state and/or federal regulatory agency requirements and good clinical practice (GCP) guidelines.

During the course of the study, monitoring visits will be conducted according to a written Monitoring Plan. The Investigator must provide sufficient time for the monitor to inspect subject medical records, source documents, case report forms, Study Medication accountability records, and regulatory documents.

Key trial personnel must be available to assist the monitor. Although the Principal Investigator must give monitors access to relevant hospital or clinical records, to confirm their consistency with the CRF entries, no information in these records about the identity of the subjects will leave the study site. Monitoring standards require full verification for the presence of informed consent, adherence to the inclusion/exclusion criteria, and documentation of all AEs, SAEs and the recording of efficacy and safety variables.

Checks of the consistency of the source data with the CRFs are performed according to the study specific Monitoring Plan. Monitoring Reports will include a summary of what the monitor reviewed as well as complications, significant findings, deviations and deficiencies, conclusions, and actions taken or to be taken to ensure site compliance.

A Study Monitoring Plan will be submitted to FDA prior to the first subject treated.

18.0 Quality Assurance

18.1 Subject Completion

Any subject who does not return for a scheduled follow-up evaluation will be contacted by telephone by the Principal Investigator, or his or her designee, to determine the cause for the missed appointment. Two telephone calls will be made and documented in the study binder, in addition to sending a certified letter requesting the subject to contact the office and return for his/her evaluation. If a returned letter receipt or an undeliverable response is received, this notice will be retained in the subject's study binder that will note the subject is lost to follow-up. If the study subject wishes to withdraw from the study, the reason(s) for discontinuation will be recorded in the subject's chart and on the appropriate CRF, if the subject gives a reason. If a significant symptom or adverse event is associated with discontinuation, this will be recorded on the CRF as well.

18.2 Data Management

Data is to be managed in accordance with a written Data Management Plan which is to be retained as described in **Section 16.4.3** of this protocol. A detailed data Monitoring Plan will be submitted to FDA prior to the first subject treated.

18.3 Quality of Data

Subject CRFs will be collected and reviewed for completeness and accuracy, as well as for any evidence suggesting subject risk. Data will be compared to source documents within the Investigator's site. Where any discrepancies are noted, the discrepancy will be resolved with the Investigator and/or an individual designated by the Investigator. When the data are incomplete, attempts will be made to obtain the missing data.

